- Secondary Aim: Determine the durability of TheraBracelet's instant effect over a month. TheraBracelet's instant effects will be quantified as an increase in the hand touch sensation score, dexterity score, and grip strength with vibration turned on vs. off (with 'on' and 'off' tested in a random order) in each weekly evaluation. Hypothesis: TheraBracelet's instant effects in improving hand function will persist across all weekly evaluations (i.e. desensitization to vibration will not occur during extended daily use over a one-month period). In addition, the broader impact of TheraBracelet will be assessed by comparing self-reported abilities for activities of daily living and quality of life between the treatment and control conditions.

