- **Durability:** The durability of TheraBracelet's instant effect will be examined by assessing TheraBracelet's instant effect in each weekly evaluation and comparing them across. The instant effect will be quantified as increase in the hand touch sensation (Monofilament Test) dexterity scores (Nine Hole Peg and Box and Block Tests) with vibration turned on compared to off, with the 'on' and 'off' tested in a random order, blinded, within a single evaluation session. If TheraBracelet's instant effect is seen for all evaluation times, it will support durability (i.e. desensitization to vibration does not occur). In addition, the impact of TheraBracelet on stroke survivors' self-reported abilities for activities of daily living and quality of life will be assessed. Specifically, the Stroke Impact Scale, SIS (sections of the hand, activities of daily living, and recovery), and Stroke Specific Quality of Life, SS-QoL (sections of the self-care and upper extremity function), will be obtained at weekly evaluations and compared between the two conditions. The Nine Hole Peg and Box and Block Tests will be videoed to ensure the exact start and stop time are recorded. This video will not include the participant's face in order to maintain confidentiality.
- **Protection against risk:** For fatigue, frequent sufficient breaks will be provided to participants. As for potential skin irritation due to wearing the wristband, the wristband tightness may be adjusted with a new wristband to maximize participant comfort. Participants will be notified if we learn anything that might make them change their mind about participating in the study. Potential risks of deterioration of hand sensation, strength, and dexterity, increased upper limb pain level and spasticity level, and/or wrist skin irritation will be monitored every week during the weekly evaluation when participants come to the laboratory. In fact, these events are the outcome measures of safety for the primary aim of the study. Participants will be informed that they can drop out of the study any time without penalty.

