- For the secondary outcome of durability of TheraBracelet’s instant effect, the hypothesis will be tested using repeated measures ANOVA for each hand function measure, with factors of vibration (on/off), condition (treatment/control), evaluation time (1-5), and their interactions. A significant main effect of vibration, with improved hand function with vibration on vs. off, with non-significant interactions of vibration×evaluation time and vibration×condition, would indicate durability over a month. In contrast, a lesser extent or abolishment of the instant effect toward the later evaluations or for the treatment condition, with significant interactions of vibration×evaluation time or vibration×condition, would indicate desensitization. In that case, the time point at which the instant effect wanes will be examined using Tukey type posthoc pairwise comparisons.
- A possibility exists that instant enhancement of hand function with TheraBracelet may trigger more use of the affected hand in daily living, which, when accumulated over time, might lead to improvement of the innate hand function (without vibration). This is analogous to cane users who may walk more with canes than without, and thus build greater lower limb abilities over time. Thus, change in the innate hand function will be examined. A significant effect of condition×evaluation time, with greater improvement of the innate hand function for the treatment vs. control, will suggest a therapeutic effect of TheraBracelet for secondary investigation.
- Impact of TheraBracelet on activities of daily living and quality of life will be assessed using repeated measures ANOVA for the SIS and SS-QoL, with the main effect of condition.

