- Power analysis: The sample size for the primary outcome of safety was determined for testing hypothesis of non-inferiority using a 2×2 crossover at 80% power and 5% significance level. A sample size of 24 (12 in each condition at randomization) provides sufficient power to conclude non-inferiority within a difference in adverse events of 20% between the discordant pairs (those who are safe with control but unsafe with treatment vs. those with the opposite), assuming a total of 10% discordance rate (proportion of participants with different responses for the two conditions) and a 90% safe rate for the control. That is, we will be powered to statistically conclude non-inferiority (hence safety) if 3 or less out of 24 participants have adverse events in treatment vs. control. For the Secondary Aim involving repeated measures ANOVA, with the effect size of $f=0.25$ for the Box and Block from our previous study, (Seo et al., 2014) a sample size of 19 is needed assuming a conservative correlation of 0.3 across evaluation times, for 80% power and 5% significance level. Thus, we will aim to obtain data from 24 participants. Considering that some may be found ineligible after enrollment, a total of 30 recruitment is proposed.
- Data sharing: Only de-identified coded data will be reported and/or shared with the public in publications, in ClinicalTrials.gov, or upon written request.

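### The durability rule relies on non-significant interactions and a pooled main effect, so an instant effect that is gone by week 4 of treatment can still be called durable

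*Combined protocol and SAP*

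**What the plan says.** Three sections describe durability, and they do not set the same test.

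- **Section 1.0, Secondary Aim.** The hypothesis is that "TheraBracelet's instant effects in improving hand function will persist across all weekly evaluations".
- **Section 9.0, Durability.** The on-minus-off effect is assessed at each weekly evaluation and compared across them: "If TheraBracelet's instant effect is seen for all evaluation times, it will support durability". No test is given, and the condition in which this is judged is not stated.
- **Section 10.0, Statistical analysis.** Each hand function measure goes into a repeated measures ANOVA "with factors of vibration (on/off), condition (treatment/control), evaluation time (1-5), and their interactions". A significant main effect of vibration in the favourable direction, "with non-significant interactions of vibration×evaluation time and vibration×condition, would indicate durability over a month". A significant two-way interaction of either kind, reflecting a smaller effect later or under treatment, indicates desensitisation. Individual time points are examined only then: "In that case, the time point at which the instant effect wanes will be examined using Tukey type posthoc pairwise comparisons".

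For the power of this aim, section 10.0 takes f = 0.25 for the Box and Block Test, 80% power and 5% significance, and states that "a sample size of 19 is needed assuming a conservative correlation of 0.3 across evaluation times". It does not say which effect this covers. The planned number is 24.

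**The concern.** A non-significant interaction says only that a change was not detected. With 24 participants and no margin for acceptable loss, it cannot stand as evidence that the effect persisted.

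The main effect does not repair this. It averages ten condition-by-evaluation cells. Five belong to the control month, and a sixth is evaluation 1 of the treatment month, before daily exposure in that condition. It can therefore remain significant after the effect has gone in late treatment.

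Loss caused by daily exposure is a vibration×condition×time pattern. That term is in the model but not in the decision rule. The two interactions in the rule mix the affected cells with unaffected ones.

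When neither interaction is significant, section 10.0 specifies no visit-level check, so the criterion in section 9.0 is never examined in exactly the case where durability is declared. The two sections can give opposite answers on the same data. What is at stake is the secondary conclusion about a month of use; the primary safety and feasibility conclusions do not depend on it.

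**Working it through.** **1. The stated sample size.** For a within-subject factor with m repeated measures, λ = f²·N·m/(1−ρ), with m−1 and (N−1)(m−1) degrees of freedom. With f = 0.25 and ρ = 0.3 (section 10.0), the N for 80% power is:

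| m | 2 | 4 | 5 | 10 | 20 |
|---|---|---|---|---|---|
| N | 46 | 32 | 28 | 19 | 13 |

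The figure of 19 reproduces as an omnibus test over 10 measures (power 0.814). That test has 9 degrees of freedom and is not one of the tests in the durability rule. A one-degree-of-freedom test with m = 5 gives 20, so the origin of 19 is inferred, not established.

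**2. Set-up for the rule.** From the documents: N = 24, 2 conditions, 5 evaluations, 5% tests. Assumptions not in the documents: f = 0.25 means an on-minus-off effect of 0.5 SD; one correlation ρ applies to all measurements (the plan gives 0.3 across evaluation times only); any loss occurs only under treatment; no dropout. Each on-minus-off difference then has variance 2(1−ρ), which is 1.4 at ρ = 0.3.

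**3. Effect absent at week 4 of treatment only, ρ = 0.3.**
- Main effect: mean over ten cells 0.45; λ = 24 × 0.45² / (1.4/10) = 34.7; power about 100%.
- Vibration×time: evaluation means averaged over conditions are 0.5 four times, then 0.25; sum of squared deviations 0.05; λ = 24 × 0.05 / 0.7 = 1.71; power 14.6%.
- Vibration×condition: condition means 0.4 and 0.5; λ = 24 × 0.1² / (2 × 1.4/5) = 0.43; power 9.6%.
- Declared durable: 1.00 × (1 − 0.146) × (1 − 0.096) = 77%.

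**4. Linear fade to zero by week 4 of treatment, ρ = 0.3.**
- Main effect: mean 0.375; λ = 24 × 0.375² / 0.14 = 24.1; power 99.7%.
- Vibration×time: means 0.5, 0.4375, 0.375, 0.3125, 0.25; sum of squares 0.0391; λ = 24 × 0.0391 / 0.7 = 1.34; power 12%.
- Vibration×condition: difference 0.25; λ = 24 × 0.25² / 0.56 = 2.68; power 35%.
- Declared durable: 0.997 × 0.88 × 0.65 = 57%.

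A constant effect is declared durable in about 0.95 × 0.95 = 90%. Simulation with 20,000 replicates agrees with these closed-form results.

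**5. Dependence on the correlation.** Probability of declaring durability:

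| ρ | 0.3 | 0.5 | 0.7 | 0.8 | 0.9 |
|---|---|---|---|---|---|
| Lost at week 4 only | 77% | 71% | 58% | 43% | about 14% |
| Linear fade to zero | 57% | 46% | 25% | 11% | under 1% |

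Half the effect lost linearly gives 82%, 71% and 61% at ρ = 0.3, 0.7 and 0.8.

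**6. N for 80% power against the linear fade.**

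| ρ | 0.3 | 0.5 | 0.7 | 0.8 |
|---|---|---|---|---|
| Vibration×time | 216 | 154 | 93 | 63 |
| Vibration×condition | 73 | 53 | 33 | 23 |

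**7. A direct look at week 4 of treatment.** The standard error is √(1.4/24) = 0.242 at ρ = 0.3, so the 95% interval has half-width 2.069 × 0.242 = 0.50 SD. A two-sided paired test wrongly shows a favourable effect in about 2.5% of trials when there is none.

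**The case against.** The strongest reply is that the size of the problem rests on assumptions outside the documents. The correlation of 0.3 is called conservative and is given across evaluation times, whereas the on/off correlation within one session governs these tests and could be higher. This stands: no single percentage should be quoted as the error rate. It does not rescue the rule, which at no value of ρ requires an effect at the last treatment visit.

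The rule is also not blind to broad loss. If the effect is absent at all of weeks 1 to 4 of treatment, durability is declared in 24% of trials at ρ = 0.3 and 2% at ρ = 0.7. That is fair, but late or gradual loss is what desensitisation over a month would look like.

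The missing three-way term should not be overemphasised. For treatment-only loss it has the same power as vibration×time (12% for the linear fade at ρ = 0.3), and adding it to the rule still leaves 50% declared durable. A longer list of non-significant terms is no cure; estimates are needed.

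Section 10.0 can be read as the operational form of section 9.0, which never defines when an effect counts as seen. That makes part of the conflict under-specification. Even so, section 10.0 implements the weekly comparison only through interaction tests. Finally, the plan never claims that 19 powers the interactions; leaving that test unnamed is, by itself, only missing detail.

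**Conclusion.** The concern holds and should be fixed. The section 10.0 rule can declare durability when the instant effect has disappeared by week 4 of treatment, which conflicts with the hypothesis in section 1.0 and the criterion in section 9.0.

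Under the stated assumptions at ρ = 0.3, a total loss at week 4 is called durable nearly as often as a constant effect (77% against 90%). With high correlation the rule performs much better, particularly against a gradual fade. The logical defect does not depend on the correlation; its practical size does. The illustration models one measure, while the plan applies the rule to each hand function measure. The issue is confined to the secondary aim.

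**What to change.** 1. Report non-significant interactions as desensitisation not detected, not as durability.
2. Base the durability statement on estimates with 95% confidence intervals: the treatment-condition on-minus-off effect at each evaluation, its change from evaluation 1 to evaluation 5, and the vibration×condition×time contrast. Report them whether or not any interaction is significant.
3. Before claiming that the effect is present at one month, require at least that the evaluation-5 interval under treatment excludes zero in the favourable direction. Describe this as presence at week 4, not as an undiminished effect. A claim of undiminished effect would need a retention margin stated in advance.
4. Reconcile sections 9.0 and 10.0, and state in which condition and by what test the effect is judged at all evaluations. The choice matters. If significance is required at every visit, a constant effect passes 3% of the time at ρ = 0.3 in the treatment condition alone and 33% pooled over conditions, but the pooled version also passes a total week-4 loss 12% of the time (55% at ρ = 0.7).
5. Name the test behind the 19, and do not present it as power for the durability interactions.

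The cost is wording only, with the same data and model. The price is more inconclusive results:

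| ρ | 0.3 | 0.5 | 0.7 | 0.8 |
|---|---|---|---|---|
| Constant 0.5 SD effect meets the week-4 criterion | 51% | 65% | 86% | 96% |
| Half-lost effect (0.25 SD) also meets it | 17% | 22% | 33% | 46% |

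Intervals will be wide. From ρ = 0.3 to 0.8, the half-width falls from 0.50 to 0.27 SD for the week-4 effect, and from 0.71 to 0.38 SD for the change between evaluations 1 and 5.

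### A significant fall in the on-minus-off difference is labelled desensitization without asking whether vibration-on scores fell or vibration-off scores rose more

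*Combined protocol and SAP*

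**What the plan says.** Section 9.0 (Durability) defines the instant effect as the gain in a hand function score "with vibration turned on compared to off, with the 'on' and 'off' tested in a random order, blinded, within a single evaluation session". It adds that if the "instant effect is seen for all evaluation times, it will support durability (i.e. desensitization to vibration does not occur").

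Section 10.0 (statistical analysis of durability) plans a repeated measures ANOVA "with factors of vibration (on/off), condition (treatment/control), evaluation time (1-5), and their interactions". A significant vibration main effect "with non-significant interactions of vibration×evaluation time and vibration×condition, would indicate durability over a month". In the other direction, the section considers "a lesser extent or abolishment of the instant effect toward the later evaluations or for the treatment condition". Its verdict on such a pattern is that this, "with significant interactions of vibration×evaluation time or vibration×condition, would indicate desensitization". Tukey-type pairwise comparisons then locate the time at which the effect wanes.

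The next bullet of section 10.0 raises the possibility that more use of the hand "might lead to improvement of the innate hand function (without vibration"). It plans a separate condition×evaluation time test of vibration-off scores, which, "with greater improvement of the innate hand function for the treatment vs. control, will suggest a therapeutic effect of TheraBracelet for secondary investigation".

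**The concern.** The instant effect is a difference between two scores, and both can move. The desensitization rule looks only at the difference, and the Tukey follow-up asks when it shrank, not which score moved. Yet the same section expects that vibration-off function may improve, and more so in the treatment condition. If vibration-off scores catch up while vibration-on scores gain less, for instance because they are near a ceiling, the plan's wording names a loss of response to vibration as the cause. The data would not have shown that.

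The plan gives no reading for the case where the vibration interaction and the innate-function test are both significant. Section 9.0 also has its own criterion, an effect present at every evaluation. A reduced but still present effect could meet that criterion and support durability, while section 10.0 calls the same data desensitization. At stake is the stated conclusion of the secondary aim.

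**Working it through.** **The plan's own figure.** The power analysis in section 10.0 gives 19 participants for this ANOVA (f = 0.25, correlation 0.3, 80% power, 5% level). With λ = n·m·f²/(1−ρ) and m = 10 measurements, λ = 19 × 10 × 0.0625/0.7 = 16.96 on 9 and 162 df, and power is 0.814. A 1-df effect with m = 5 also gives 19 (λ = 8.48, power 0.819). The document does not say which was used. The figure reproduces, and the point does not depend on it.

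**What the interaction can see.** Orient scores so that higher is better. Let D = On − Off at a visit. Then change in D = change in On − change in Off. Vibration×evaluation time and vibration×condition are tests on D alone.

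| Change from evaluation 1 to 5, treatment month (assumed) | Off | On | D |
|---|---|---|---|
| Only vibration-on falls | 0 | −3 | −3 |
| Only vibration-off rises | +3 | 0 | −3 |
| Off rises more than on | +3 | +1.5 | −1.5 |
| Equal gains | +3 | +3 | 0 |

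The first two rows give the same D, so the planned tests cannot tell them apart. The last row leaves D unchanged.

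**A Box and Block example (assumed scores).** At evaluation 1, off 20 and on 24, so D = 4. At evaluation 5, either off 24 and on 26 (D = 2) or off 20 and on 22 (D = 2). The reduction is the same. In the first case performance with vibration rose by 2 and without it by 4. In the second, vibration-on fell by 2. In both, on still exceeds off at the two visits shown; if that held at every visit, section 9.0's criterion would point to durability.

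**How often the label would appear.** Assumptions, none from the documents except n = 24: instant effect 3 points, residual SD 3, between-subject SD 12, linear change in the treatment month only, 2,000 runs. The label is given if either interaction is significant at 5% and D is smaller at evaluation 5 than at 1, or smaller in treatment than in control.

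| Off / on gain | Label given | Innate test significant | Both |
|---|---|---|---|
| 0 / 0 | 5% | 6% | 0.4% |
| +3 / +3 | 4% | 55% | 2% |
| +3 / +1.5 | 32% | 55% | 17% |
| +3 / 0 | 81% | 56% | 45% |
| 0 / −3 | 82% | 5% | 4% |
| +1 / 0 | 19% | 10% | 2% |

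The 81% and 82% differ only by simulation error (standard error √(0.81 × 0.19/2000) ≈ 0.9 percentage points).

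**Analytic check of vibration×condition in the +3 / 0 row.** D in treatment runs 3, 2.25, 1.5, 0.75, 0, mean 1.5, against 3 in control: a difference of 1.5. Its standard error is 3 × √2 × √(2/5)/√24 = 0.548, so the noncentrality is 1.5/0.548 = 2.74. On 23 df the power is 0.75, against 0.74 simulated.

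**Does the innate-function test rescue the reading?** In the +3 / 0 row, 81% − 45% = 36% of runs carry the label without a significant innate result. In the other 45% both results appear, and the plan does not say how to read them together.

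**The case against.** The best defence is that the rule is narrower and better controlled than it may look.

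- A reader might infer that any shrinkage is called desensitization. It is not: section 10.0 requires a significant interaction.
- A reader might infer that improved innate function, or practice over ten visits, would itself be reported as loss of effect. The documents do not support that. On and off are tested in random order, blinded, in one session, so practice is shared by both states; a gain carried into both leaves D unchanged and is read correctly (4% labelled). The innate-function bullet does not say that vibration-on scores would lag.
- A reader might infer that the plan ignores vibration-off function. It tests it separately, so a rise is looked for.
- The same-session off score is the proper control for the device's added benefit. Off 20 / on 24 moving to off 24 / on 26 also fits true desensitization on a shared gain of 4: on should have reached 24 + 4 = 28 and reached 26. So the example does not prove a false verdict, and declaring such cases free of desensitization would be just as unfounded.
- A ceiling is only a possibility. Section 4.0 sets no upper limit on Box and Block and requires no sensory deficit, but the documents give no baseline scores.
- Reduced added benefit and improved innate function can coexist, so declaring both is not in itself a contradiction.

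All of this stands, and it limits the point. It does not remove it: when vibration-off scores rise more than vibration-on scores, the rule names a cause that the interaction cannot identify, and nothing links the innate-function result to that reading.

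**Conclusion.** The concern holds in a limited form. A significant interaction with a smaller D shows that the added effect of vibration has fallen. It does not show that this is desensitization, because a greater rise in vibration-off than in vibration-on scores gives the same result. The problem arises only when vibration-off scores outgain vibration-on scores; with equal gains the rule works.

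That identity is algebraic and needs no assumption. The 81% against 82% rests on the assumed SDs, effect and gains, and smaller catch-up is labelled less often (32% for +3 / +1.5, 19% for +1 / 0). The documents do not show that catch-up will occur.

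This concerns the interpretation of a secondary outcome. It does not touch the safety or feasibility analyses or the sample size. It should be changed, and before unblinding, because choosing the reading after seeing which score moved would be post hoc.

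**What to change.** In the durability bullet of section 10.0:

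1. Read a significant vibration×evaluation time or vibration×condition interaction with a smaller difference as a *reduced instant effect*.
2. Tabulate vibration-on and vibration-off means, with confidence intervals, by evaluation and condition for each measure.
3. Attribute the reduction to desensitization only when vibration-off scores are stable (or change no more in treatment than in control) and vibration-on scores fall or are lower in treatment than in control.
4. Where vibration-off scores rose and vibration-on scores did not fall, report *reduced increment, cause not distinguished*, using the control month to gauge practice. State that this reading also applies when the innate-function test is significant.
5. Do not relabel such cases as durability or as absence of desensitization.
6. Align the section 9.0 criterion with this, so that an effect that is present but significantly reduced gets one reading.

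A simpler rule, requiring both a fall in vibration-on scores and no rise in vibration-off scores before the word desensitization may be used, would be unsafe: on a background of practice gains it would hide a true loss of response.

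Cost: a few sentences and one more table per measure, with no new data. Some significant interactions will be left without a stated cause.

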9.0 Study Design / Methods

- **Study design:** The study will use a 2×2 crossover design. Participants will be randomly assigned to either the treatment or control condition for the first month, followed by a 2-week washout period and then crossover to the other condition. For both conditions, participants will be instructed to wear TheraBracelet on the affected wrist every day for at least 8 hours/day during their daily activity over a month. The device will apply wrist vibration at 60% of the sensory threshold (imperceptible) for the treatment condition, and no vibration for the control condition. The control condition is needed to assess safety of TheraBracelet in comparison to that of simply wearing a wristband, thereby accounting for any worsening of symptoms that may occur as a natural course after stroke. Half the participants will start with the treatment and half with the control (balanced).
- **Schedule:** One person's participation will be 2.5 month long (= 1 month for one condition, 2 week washout period, 1 month for another condition). For each condition, participants will come to the laboratory once a week for evaluation for a total of 5 times: The 1st visit will entail the baseline evaluation followed by an introduction to using the device. Subsequent visits will be for evaluation after using the device each week. A follow-up assessment will be administered 4-16 weeks after the 10th session if any safety measure has worsened as defined as an adverse event by the 10th visit compared to the 1st visit. The follow-up assessment will evaluate only the measure that has worsened.
- Evaluation will include feasibility, safety, and durability, as detailed below.

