detectable change (MDC) (also known as the smallest real difference, Chen et al 2009). Hand dexterity will be determined to have deteriorated if the Nine Hole Peg or Box and Block Test score worsens by more than 20% (approximately 2 standard deviation of the population data) and MDC (Chen et al 2009). Hand strength and dexterity measurement will be performed three times during the baseline testing. Upper limb pain will be assessed using the visual analog pain rating scale (0 to 10). Upper limb pain will be determined to have increased if the pain level indicated on the visual analog pain rating scale increases by more than 2. Spasticity will be show assessed using the Modified Ashworth Scale (MAS). Spasticity will be determined to have worsened if MAS increases by more than 1 point (equivalent to the effect size of botulinum toxin A). Wrist skin irritation and increased swelling, if there is any, will be noted. Rigorous safety criteria will be used in which adverse events will be noted if any of the measures (hand sensation, strength, dexterity, pain, spasticity, skin irritation, swelling) worsens at any of the four evaluation times compared to the baseline. The co-investigator and study neurologist, [name], will meet with each participant in person or via teleconference to interview the participant regarding safety related to wearing the device.

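### The plan does not say which evaluations enter the SIS and SS-QoL condition effect; if the pre-device evaluation is one of them, the estimate is 0.8 of the mean on-device effect

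*Combined protocol and SAP*

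**What the plan says.** The whole SIS and SS-QoL analysis in section 10.0 is that impact is assessed "using repeated measures ANOVA for the SIS and SS-QoL, with the main effect of condition". It gives no set of evaluations, time factor, interaction or baseline adjustment.

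Section 9.0 (Schedule) says that for each condition "participants will come to the laboratory once a week for evaluation for a total of 5 times". It adds that "The 1st visit will entail the baseline evaluation followed by an introduction to using the device", and then that "Subsequent visits will be for evaluation after using the device each week". Evaluation 1 of each month is therefore taken before device use, and evaluations 2-5 after it has begun. Section 9.0 (Durability) has the SIS and SS-QoL sections obtained at weekly evaluations.

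Two other analyses in section 10.0 do state how time is handled. The durability ANOVA has factors of vibration, "condition (treatment/control), evaluation time (1-5), and their interactions". Innate hand function is judged by "A significant effect of condition×evaluation time, with greater improvement of the innate hand function" in the treatment condition.

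**The concern.** A main effect of condition averages the treatment-control difference over every evaluation in the model. Before month 1's device use there can be no condition effect, and without carryover the same holds before month 2. If evaluation 1 is included, it adds a zero to that average.

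The innate hand function test does not have this difficulty: in a condition-by-time interaction, evaluation 1 is the starting point from which change is measured. In a main effect it can only dilute.

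At stake is the plan's only between-condition comparison of self-reported daily function and quality of life. The published effect could be about one-fifth too small and less likely to be detected. While the set of evaluations is open, it could also be chosen after the data are seen.

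**Working it through.** **1. Which evaluations does the text imply?**

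- *All five.* The Schedule counts five once-a-week evaluations. The Durability text assesses the instant effect at each weekly evaluation, and section 10.0 analyses that over times 1-5.
- *On-device only.* The Feasibility text in section 9.0 has participants hand in the usage log at the weekly evaluation, and staff note which hand wears the device when it begins. Neither fits a visit held before the device is introduced. The Safety text counts an adverse event if a measure "worsens at any of the four evaluation times compared to the baseline", which separates four visits from the baseline.

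The term is used both ways.

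**2. The plan's own figure.** The documents give no effect size or power for SIS or SS-QoL. The nearest figure is N = 19 for the Secondary Aim ANOVA (f = 0.25, correlation 0.3, 80% power, 5% level). Use a noncentral F with m repeated measures, λ = N·f²·m/(1−ρ), and df m−1 and (N−1)(m−1). Then m = 10 (2 × 5 evaluations) gives N = 19 with power 0.814, while m = 8 (2 × 4) needs N = 22. This fits five evaluations, but it concerns Box and Block and is only indirect evidence here.

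**3. Dilution if all five enter.** Let d1 to d4 be the condition effects at evaluations 2-5, with mean d. With equal weights, complete data and no carryover:

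(0 + d1 + d2 + d3 + d4)/5 = 4d/5 = 0.80 d, whatever the weekly pattern.

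Simulation with a true effect of 1 gave 0.799 for five evaluations and 0.996 for evaluations 2-5.

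**4. Carryover to month 2's first evaluation only.** Let a fraction c of d remain there. It affects the control month of the treatment-first half, so the mean difference at evaluation 1 is −c·d/2. The five-evaluation effect is d(4 − c/2)/5:

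- c = 0: 0.80 d
- c = 0.5: 3.75/5 = 0.75 d
- c = 1: 3.5/5 = 0.70 d

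Evaluations 2-5 give 1.00 d in each case.

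**5. Carryover through all of month 2.** Five evaluations give 0.8 − c/2 and evaluations 2-5 give 1 − c/2. At c = 0.5 these are 0.55 and 0.75, so both are biased.

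**6. Power (all inputs assumed for these scales).** With n = 24, outcome SD 1, k evaluations per month, and within- and between-month correlations w and b:

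SE = √(2[(w − b) + (1 − w)/k]/24).

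At w = b = 0.3 and an effect of 0.3 SD, five evaluations give 0.24/0.108 = 2.22 and evaluations 2-5 give 0.30/0.121 = 2.48. Noncentral t power, two-sided 5%, is shown as five evaluations (23 df) / evaluations 2-5 with a period term (22 df):

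| w / b | 0.2 SD | 0.3 SD | 0.4 SD | 0.5 SD |
|---|---|---|---|---|
| 0.3 / 0.3 | 0.295 / 0.354 | 0.567 / 0.661 | 0.810 / 0.886 | 0.943 / 0.977 |
| 0.7 / 0.6 | 0.264 / 0.354 | 0.513 / 0.661 | 0.756 / 0.886 | 0.912 / 0.977 |
| 0.8 / 0.6 | 0.192 / 0.263 | 0.369 / 0.511 | 0.582 / 0.754 | 0.773 / 0.911 |
| 0.8 / 0.7 | 0.295 / 0.402 | 0.567 / 0.727 | 0.810 / 0.928 | 0.943 / 0.990 |

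The loss runs from about 3 points (0.3/0.3, 0.5 SD) to about 17 (0.8/0.6, 0.4 SD). The period term itself costs little: at 0.3/0.3 and 0.3 SD, evaluations 2-5 without it have power 0.663, against 0.661 with it.

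**7. Type I error.** With no effect, every term in the average is zero under either choice. Simulated false-positive rates for the participant-level tests were 0.047-0.051.

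**The case against.** The strongest objection is that the harm depends on a reading the plan does not state. The Feasibility text uses weekly evaluation for visits at which the device has been worn, and the Safety text separates four evaluation times from the baseline. On that reading nothing is diluted. The times 1-5 belong to the durability ANOVA, whose vibration on/off contrast is meaningful at evaluation 1, and the N = 19 calculation is for Box and Block. All of this stands. A reader might infer that the plan commits itself to averaging in the pre-device visit; the documents do not support that, and the 0.8 factor is conditional.

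The power figures are also open to challenge. The 0.3 correlation is given for the Box and Block calculation, and no effect size is given for SIS or SS-QoL. Only the range is informative, and the 0.8 factor does not need it.

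Finally, this is a supporting analysis with no decision rule or power claim, and the bias is conservative. That limits the severity. It does not remove the point: the omission is in the text, the schedule and companion ANOVA lean toward five evaluations, and naming evaluations 2-5 gives a better estimate at almost no cost.

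**Conclusion.** The point holds in conditional form. The plan leaves the set of evaluations open. If evaluation 1 enters, the condition effect is 0.80 of the mean effect over evaluations 2-5, assuming equal weights, complete data and no carryover, or 0.70-0.75 if half to all of the effect remains at month 2's first evaluation only. The factor is relative to the average over the four on-device visits, not to the effect at week 4.

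A reader might go further and infer a false-positive problem or a threat to the trial's main conclusions. Neither follows: the dilution pulls toward no effect, and safety and feasibility are analysed separately. Nor would the change make a null result conclusive at modest effects; at 0.3 SD and correlation 0.3, power is only 0.661 after it. Minor severity; a cheap improvement.

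**What to change.** State in section 10.0 that the SIS and SS-QoL condition effect is estimated on evaluations 2-5 of each month. One way is the within-participant difference between months in the evaluation 2-5 mean, with a period term.

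The cost is SAP wording, one degree of freedom (23 to 22) and about 0.2 points of power. No new data are needed and no on-device data are lost.

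Any adjustment for each month's evaluation 1 should be supporting only, because carryover can reach that covariate. If half the effect remains at month 2's first evaluation and not later, the adjusted estimate is too large by [(w − b)/(1 − b)]·c/2. With c = 0.5 that is 0.25 × 0.25 = 6.3% at correlations 0.7/0.6, 0.5 × 0.25 = 12.5% at 0.8/0.6, and 0.333 × 0.25 = 8.3% at 0.8/0.7.

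The SAP should also say that using evaluations 2-5 does not remove bias from carryover that persists through month 2.
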